**Phase II cohort definitions and expectations**

Differences in the natural history of the lymphoma subtypes allowed on this clinical trial will require stratification. Therefore, we will separate accrued patients into three independent cohorts. As this is the first detailed evaluation of TAK228 in relapsed lymphoma, we will employ a bayesian trial design to avoid potential futility and/or toxicity.

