### **Phase II design:**

During the phase II study, patients will be treated with TAK228 at the MTD established in the sponsored trials. Three independent cohorts of patients will be enrolled: 1) patients with aggressive lymphoma (diffuse large B cell lymphoma, follicular grade 3b, transformed lymphomas, and mantle cell lymphoma); 2) patients with indolent lymphoma (follicular lymphoma grade 1 – 3a, small lymphocytic lymphoma, and marginal zone lymphoma); and 3) patients with Hodgkin lymphoma. We will run the three cohorts as three parallel trials. The maximum number of patients needed for each cohort is 25.

For each of the patient cohort, the overall response (OR) at two cycles and dose modifications required based upon toxicity (referred to below as reason for dose modification) at one cycle will be monitored. Simultaneously using Bayesian stopping boundaries calculated based on Beta-Binomial distributions. Independence was assumed between OR and Reason for dose modification.

For each of the patient cohort, the overall response (OR) at two cycles and dose modifications required based upon toxicity (referred to below as reason for dose modification) at one cycle will be monitored. Simultaneously using Bayesian stopping boundaries calculated based on Beta-Binomial distributions. Independence was assumed between OR and reason for dose modification.

For cohorts A) and H), TAK228 will be considered promising if it yields an OR rate of 35% at two cycles and a reason for dose modification rate of 30% at one cycle. A sample size of 25 in each patient cohort ensures that, if the cohort is not terminated early, a posterior 90% credibility interval for overall response rate will have width of 0.297 at most, under the assumption of a 35% of OR rate. The prior probabilities of OR and reason for dose modification for the experimental regimen are modeled by beta distributions (*Beta*(0.7,1.3) and *Beta*(0.6,1.4), respectively). Denoting probabilities of OR rate and reason for dose modification rate by (pOR , pReason for dose modification) Confidential, the following decision criteria will be applied: Stop the trial if  $\text{Prob}(pOR < 35\% | \text{data}) > 0.95$  or  $\text{Prob}(p\text{Reason for dose modification} > 30\% | \text{data}) > 0.95$ .

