Patients will be monitored by a cohort size of 5 after the first 15 patients according to the following stopping boundaries for OR at two cycles and reason for dose modification at one cycle. If the number of responses required for moving the trial to next stage has not been achieved, the patient enrollment will be halted until enough responses observed.

For cohorts I), TAK228 will be considered promising if it yields an OR rate of 45% at two cycles and a REASON FOR DOSE MODIFICATION rate of 25% at one cycle. A sample size of 25 ensures that, if the cohort is not terminated early, a posterior 90% credibility interval for overall response rate will have width of 0.310 at most, under the assumption of a 45% of OR rate. The prior probabilities of OR and REASON FOR DOSE MODIFICATION for the experimental regimen are modeled by beta distributions ( $Beta(0.9,1.1)$  and  $Beta(0.5,1.5)$ , respectively). Denoting probabilities of OR rate and REASON FOR DOSE MODIFICATION rate by ( $p_{OR}$ ,  $p_{Reason\ for\ dose\ modification}$ ), the following decision criteria will be applied: Stop the trial if  $Prob(p_{OR} < 45\% \mid data) > 0.95$  or  $Prob(p_{Reason\ for\ dose\ modification} > 25\% \mid data) > 0.95$ .

Patients will be monitored by a cohort size of 5 after the first 15 patients according to the following stopping boundaries for OR at two cycles and REASON FOR DOSE MODIFICATION at one cycle. If the number of responses required for moving the trial to next stage has not been achieved, the patient enrollment will be halted until enough responses observed.

Patients who are treated on study and have at least 1 disease restaging study prior to termination of study participation will not be replaced with an additional patient added to their disease cohort. Patients who are treated on study and fail to have at least 1 disease restaging study prior to termination of study participation will be replaced with an additional patient added to their disease cohort at the discretion of the principle investigator.

The duration of the study as a whole is defined first patient to start the screening period to the last patient to conclude their therapeutic period. The anticipated accrual is 3 patients per month on this trial. Thus, accrual for the study is expected to be complete in approximately two years. The total duration of the study is anticipated to be approximately three years.

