### Population for Analysis

Data from all subjects who receive any study drug will be included in the safety analyses. Subjects who entered the study and did not take any of the study drug and had this confirmed, will not be evaluated for safety.

The patient population for efficacy analysis will include all patients who received at least one dose of study drug.

Safety and efficacy data will be reviewed after 5, 10, 15, 20, and 25 patients have completed all courses of TAK228, however, accrual will continue while this analysis is pending. If there is unacceptable study drug-related toxicity, the study will be placed on hold and no further treatment of any patient will occur until further review and discussion with the FDA. The study may proceed after appropriate amendments have been made to address the observed study drug-related toxicity.

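### The safety reviews that come before 15 patients per cohort are not timed to the one-cycle toxicity endpoint, and minimum accrual is stated as both 45 and 24

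*Combined protocol and SAP*

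**What the plan says.** The section on cohort definitions gives the purpose of the monitoring: "we will employ a bayesian trial design to avoid potential futility and/or toxicity". Under Phase II design, the toxicity endpoint is short: "dose modifications required based upon toxicity (referred to below as reason for dose modification) at one cycle will be monitored". A cycle is 28 days. Three cohorts run in parallel, and "The maximum number of patients needed for each cohort is 25".

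The numeric rule stops a cohort when the posterior probability that the dose-modification rate exceeds its limit (30% in A and H, 25% in I) is above 0.95. It shares its schedule with the two-cycle response rule: "Patients will be monitored by a cohort size of 5 after the first 15 patients according to the following stopping boundaries".

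A second mechanism appears under Population for Analysis and again under Protocol Monitoring. Safety and efficacy data are reviewed after 5, 10, 15, 20 and 25 patients have finished all their courses of drug, and "accrual will continue while this analysis is pending". Its trigger is qualitative: "If there is unacceptable study drug-related toxicity, the study will be placed on hold and no further treatment of any patient will occur".

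Estimated Accrual gives a minimum of 45 patients. Accrual Comments gives 24.

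**The concern.** The toxicity endpoint is known 28 days after a patient starts. Two mechanisms could use it. The numeric rule cannot act before 15 patients in a cohort, which is 60% of the maximum. The reviews at 5 and 10 come earlier in patient count, but they are counted on the end of treatment, which may be many months after the end of cycle 1. The cycle 1 data that would show an excess of dose modification can therefore be complete well before the review meant to look at them, while enrolment goes on.

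The two minimum accrual figures matter here because the minimum shows when a cohort can first close. A reader cannot tell from 24 where the first look lies.

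**Working it through.** **Inputs.** From Phase II design: first boundary at 15, then steps of 5, with a maximum of 25. Toxicity priors are Beta(0.6, 1.4) with limit 0.30 for A and H, and Beta(0.5, 1.5) with limit 0.25 for I. The cut-off is 0.95. Accrual is 3 patients per month for the whole trial. From Evaluation During Study: the last scheduled haemoglobin A1c test is at cycle 12 day 1. The boundary table is not in the available text, so all boundaries below are derived from the stated criteria.

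**Reproducing the plan's own figures.** The equal-tailed 90% interval of Beta(a + 25r, b + 25 − 25r), using the response priors, has width 0.2966 for A/H (r = 0.35; stated 0.297) and 0.3099 for I (r = 0.45; stated 0.310). Both agree, so the priors are read as intended.

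**Timing of the review at 10.** Assume accrual splits evenly, 3 / 3 = 1 patient per month per cohort.
- Counted on completed cycle 1: patient 10 enters at month 10 and completes 28 days at about month 11.
- Formal look at 15, on the same endpoint: about month 16.
- Counted on completed courses, if the first ten patients all stay on drug to cycle 12: at least 11 × 28 = 308 days, about 10 months, so about month 20.

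The last case is an extreme. Each patient who stops early brings the review forward. The range is therefore from about month 11 to month 20 or later, and the toxicity endpoint does not determine where in that range the review falls.

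**Minimum accrual.** 3 cohorts × 15 = 45, which matches a first look at 15. 24 / 3 = 8, and no look is stated at 8.

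**Optional formal look at 10.** The boundary is the smallest x with P(p > limit | Beta(a + x, b + n − x)) > 0.95.
- A/H, n = 10: Beta(6.6, 5.4) gives 0.962 at x = 6; x = 5 gives 0.880. Stop at 6/10, then 8/15 and 10/20.
- I, n = 10: Beta(6.5, 5.5) gives 0.983 at x = 6; x = 5 gives 0.935. Stop at 6/10, then 7/15 and 9/20.

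Stopping probabilities come from exact binomial enumeration over looks {15, 20} and {10, 15, 20}, toxicity rule only, with no patients enrolled while outcomes are awaited. Expected patients = Σ n × P(stop at n) + 25 × P(no early stop). For A/H at 50%:
- now: 15 × 0.5000 + 20 × 0.1297 + 25 × 0.3703 = 19.35
- with the look: 10 × 0.3770 + 15 × 0.1652 + 20 × 0.1106 + 25 × 0.3472 = 17.14

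| Cohort | True rate | Closes before 25: now → with look | Patients saved |
|---|---|---|---|
| A/H | 30% (acceptable) | 6.8% → 8.7% | – |
| A/H | 35% | 15.6% → 18.2% | 0.8 |
| A/H | 40% | 28.9% → 31.9% | 1.2 |
| A/H | 50% | 63.0% → 65.3% | 2.2 |
| A/H | 60% | 89.0% → 89.9% | 3.3 |
| I | 25% (acceptable) | 6.9% → 7.2% | – |
| I | 35% | 30.2% → 30.8% | 0.5 |
| I | 40% | 47.3% → 47.9% | 0.9 |
| I | 50% | 79.1% → 79.4% | 1.9 |
| I | 60% | 95.6% → 95.6% | 3.2 |

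At the acceptable rate, the look itself closes 4.7% of A/H cohorts and 2.0% of I cohorts with 10 patients.

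**The case against.** The strongest reply is that a first numeric look at 15 is a legitimate choice. The drug is not given at an untested level: "patients will be treated with TAK228 at the MTD established in the sponsored trials". A cohort closed at 10 leaves a weak basis for the response rate, which is the primary objective. An extra look barely changes whether a toxic cohort closes; it mainly changes when. All of this stands, and it is why the look at 10 is offered only as an option.

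A reader might infer that there is no toxicity protection before 15 patients. The documents do not support that. Patients are assessed weekly in cycle 1 with toxicity grading, and the periodic reviews can put the whole study on hold. A reader might also infer that the reviews at 5 and 10 always come late. They do not: a patient who leaves because of toxicity has finished treatment and counts soon. What remains is that patients who have dose modifications and stay on drug, which is what this endpoint also captures, do not count until they finish.

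Nor is there a demonstrated contradiction between halting enrolment when responses are lacking at a formal stage and continuing accrual during a periodic review. These can be two separate mechanisms. The review counts end at 25, the cohort maximum, which points to a per-cohort count, although the text does not say so. The number of courses and the operating characteristics may be given in material that is not available here, so their absence is not held against the plan.

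**Conclusion.** Two points hold. First, the scheduled safety reviews before 15 patients per cohort are triggered by the end of treatment, although the toxicity endpoint is complete at 28 days. This is a cheap improvement to make, not an error in the stopping rule. Its size depends on time on treatment, which the documents do not give: from almost no delay if patients stop early to about 9 months (month 20 against month 11) if the first ten all reach cycle 12, assuming one patient per month per cohort. Second, the two minimum accrual figures contradict each other, and 24 does not fit a first look at 15 in each of three cohorts.

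It would go too far to conclude that the plan must add a numeric look at 10. That is a trade-off: 0.5 to 3.3 patients saved per cohort at assumed true rates of 35–60%, against 1.8 points (A/H) or 0.3 points (I) more false stopping. The documents do not say that any rate in that range is likely. These results take the monitoring sentence to mean a first look at 15, as the minimum of 45 suggests. A stricter reading would put it at 20.

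**What to change.** - **Review timing.** In Population for Analysis and Protocol Monitoring, trigger the existing safety reviews at 5, 10, 15, 20 and 25 on patients who have completed cycle 1, counted per cohort. Tabulate the one-cycle dose-modification count at each review. The cost is wording plus somewhat earlier and more frequent review work. No new data are needed, because toxicity is already graded through cycle 1.
- **Minimum accrual.** Reconcile 45 (Estimated Accrual) with 24 (Accrual Comments). If the first look is at 15 in each of three cohorts, the figure that follows is 45. The cost is one correction.
- **Optional.** Apply the plan's own posterior toxicity criterion at 10 patients as well (6 or more of 10 in every cohort), leaving the response looks where they are. The cost is one boundary row, the rise in false stopping given above, and the chance that an acceptable cohort closes with only 10 patients for the response estimate. If the sponsor prefers to keep the first formal look at 15, one sentence giving the reason is enough.

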#### Randomization and Stratification

There will be no randomization in this study. Patients will be stratified only based upon the lymphoma subtype into the appropriate cohort.

### Analysis Plan

For each patient cohort, summary statistics will be provided for continuous variables such as age. Frequency tables will be used to summarize categorical variables such as gender, histology, response, toxicity type and severity. Logistic regression will be utilized to assess the effect of patient prognostic factors on the response rate and the toxicity rate. The distribution of time-to-event endpoints, such as time to progression and overall survival, will be estimated using the method of Kaplan and Meier. Comparison of time-to-event endpoints by important patient characteristics will be made using the log-rank test.

### Population for Analysis

Data from all subjects who receive any study drug will be included in the safety analyses. Subjects who entered the study and did not take any of the study drug and had this confirmed, will not be evaluated for safety.

The patient population for efficacy analysis will include all patients who received at least one dose of study drug.

Safety and efficacy data will be reviewed after 5, 10, 15, 20, and 25 patients have completed all courses of TAK228, however, accrual will continue while this analysis is pending. If there is unacceptable study drug-related toxicity, the study will be placed on hold and no further treatment of any patient will occur until further review and discussion with the FDA. The study may proceed after appropriate amendments have been made to address the observed study drug-related toxicity.

### Efficacy Analysis

Summary statistics will be provided for continuous variables. Frequency tables will be used to summarize categorical variables. Logistic regression will be utilized to assess the effect of patient prognostic factors on the response rate and the toxicity rate. The distribution of time-to-event endpoints, such as overall survival, progression free survival, and response duration, will be estimated using the method of Kaplan and Meier. Comparison of time-to-event endpoints by important subgroups will be made using the log-rank test. Cox proportional hazard regression may be employed for multivariate analysis on time-to-event outcomes.

### **Safety Analysis**

Toxicity evaluation will be based on the incidence of severity and type of adverse events (including physical and laboratory). At each cycle clinic visit, patients will have vital signs (temperature, blood pressure, heart rate, and weight) measured, ECOG performance status assessed, be asked about all toxicities they have suffered, and undergo a physical exam. In addition, routine clinical laboratory testing (complete blood count, electrolytes, kidney and liver related labs) will be performed.

Does this protocol include a dose expansion component? No

### **Data Safety Monitoring Board / DSMB at MDACC:**

Select the name of the data safety monitoring board (DSMB) monitoring this protocol:  
Not Applicable

Please explain:

This protocol is neither randomized nor blinded.

### **Protocol Monitoring:**

Does this protocol have a schedule for interim and final analysis? Yes

Provide a summary or schedule of interim analysis.

Safety and non-binding efficacy data will be reviewed after 5, 10, 15, 20, and 25 patients have completed all courses of TAK228, however, accrual will continue while this analysis is pending. If there is unacceptable study drug-related toxicity, the study will be placed on hold and no further treatment of any patient will occur until further review and discussion with the FDA. The study may proceed after appropriate amendments have been made to address the observed study drug-related toxicity. It is anticipated that a preliminary report of efficacy and safety may be presented at a national meeting such as the ASCO Annual Meeting, including the trials in progress poster session, or the American Society of Hematology Annual Meeting.

### **Protocol Monitoring Plan:**

A Bayesian dose escalation program and efficacy/toxicity monitoring to allow for cohorts which do not meet our efficacy targets to close early.

### **Intellectual Property:**

1. Does this study include any agents, devices, or radioactive compound (or No drug) manufactured at MD Anderson Cancer Center or by a contract

manufacturer?

**Investigational New Drugs (IND):**

Does this protocol require an IND? Yes

Who is the IND Holder/Regulatory Sponsor?

[UT MDACC](#)

IND Number: 129,368

Please "Compose" an Investigator's Brochure Cover Letter. For technical assistance, contact the PDOL Help Desk, [contact].

**Investigational Device (IDE):**

Does this study utilize an Investigational Device? N/A

**Immunotherapy**

Is this an Immunotherapy study? No

**Moon Shots Program**

Will your protocol be funded by the Moon Shots Program? No

**Sponsorship and Support Information:**

Does the Study have a Sponsor, Supporter or Granting Agency? Yes

Sponsor Name: Takeda Pharmaceuticals, Inc.

Support Type: Industry Funding

Agent Name(s): TAK228

This Sponsor/Supporter/Granting Agency will receive data.

**Regulatory Requirements**

**Radioactive Material:**

---

Does this study involve the administration of radioisotopes or a radioisotope labeled agent? N/A

[Click here for help](#)

---

**Biosafety:**

Does this study involve the use of Recombinant DNA Technology such as No

DNA nucleotide, RNA nucleotide, genetically modified human cells, animal cells, bacteria, or virus?

Does this study involve the use of organisms that are infectious to humans? No

Does this study involve human/animal tissue other than blood derived hematopoietic stem cells? N/A

Questions should be addressed to the Transfusion Medicine Tissue Coordinator at [contact].

**Laboratory Tests:**

Is there any biomarker testing in this study being used to determine patient/participant eligibility, treatment assignment, or management of patient/participant care?

Yes

No

Not Applicable For This Protocol

**Manufacturing:**

Will you manufacture in full or in part (split manufacturing) a drug or biological product at the M. D. Anderson Cancer Center for the proposed clinical study? No

**Student/Trainee Information:**

Is this research being conducted as a partial fulfillment for completion of a degree? No
